3.4 Study Suspension Criteria

The study will be suspended if any of the following occur:

- A treatment-associated death in a subject receiving AR201
- Two subjects hospitalized within 6 months of each other for ongoing intensive treatment due to AR201-related adverse events
- Three subjects hospitalized for ongoing intensive treatment due to AR201-related adverse event
- Greater than 2 cases of AR201-related anaphylaxis resulting in hypotension, neurologic compromise, or mechanical ventilation (systemic allergic reaction grading system grade ≥ 3 per [Section 8.6](#); clinical assessment per [Section 8.4.1](#))

Admission to the hospital for observation only (not for ongoing intensive treatment of a serious AR201-related adverse event) will not be considered contributory to the study suspension criteria. Contributory events of anaphylaxis must be documented (including signs and symptoms and a clinical assessment) and meet the protocol-specified criteria for anaphylaxis. The DSMC may also recommend stopping the study for any substantial imbalance in adverse events apart from anticipated dosing-related allergy symptoms, based on their review of the safety data.

In the event of study suspension based on the above criteria, enrollment and dose escalation will be halted. Dosing at the current tolerated dose level will continue unless otherwise directed by regulatory authorities. Study suspension will not be lifted until after the safety data are discussed with regulatory authorities and the regulatory authorities agree with resuming enrollment and dose escalation.

The sponsor may suspend the study in the event of a pandemic, epidemic, or other emergency not related to the study if the resulting restrictions do not permit conduct of the alternate procedures described in [Appendix 3](#). Study suspension will not be lifted until after consideration of individual subjects; study sites; and local, state, regional, and national guidance as applicable; and in accordance with regulatory requirements.

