Adverse event or intercurrent illness	
Subjects must discontinue early for any intolerable adverse event that may lead to undue risk if study treatment were continued, such as the following:
 
 • Life-threatening symptoms, including anaphylaxis resulting in hypotension, neurologic compromise, or mechanical ventilation related to study treatment or food challenge. • Severe dose-related symptoms that require intensive therapy (per investigator assessment, but may include interventions such as IV epinephrine, intubation, or admission to an intensive care unit) or are recurrent. 
Subjects must discontinue early for any adverse event that meets the early discontinuation criteria for study product tolerability or delays as follows:
 
 • Tolerability of study product: 
 – Dose-limiting or moderate symptoms at ≤ 1 mg or severe symptoms at any dose on initial dose-escalation day 1; dose-limiting, moderate, or severe symptoms on initial dose-escalation day 2 – Unable to reach the 300 mg/day dose within 40 weeks of up-dosing • Use of rescue medications: 
 – Treatment with epinephrine, beta-agonist, oxygen, IV fluids, > 2 doses of antihistamines, and/or glucocorticosteroids at ≤ 1 mg study product or for severe symptoms at the 2 mg dose on initial dose-escalation day 1 or 2 – Treatment with 3 or more doses of epinephrine for an event of dose-related symptoms anytime • Dose adjustment of study product: 
 – Unable to escalate the dose level after 3 consecutive failed attempts with at least 2 weeks between each escalation attempt – Unable to tolerate 3 attempts at dose reduction after mild or moderate symptoms, or unable to tolerate 1 attempt at dose reduction after severe symptoms • Missed ≥ 15 consecutive days of study product dosing due to any circumstances (eg, as part of the treatment for an intercurrent adverse event). Missed doses per dose adjustment guidelines in Section 8.7.3.2 are allowed. 
Subjects must discontinue early for any intolerable adverse event that cannot be ameliorated using adequate medical intervention or that in the opinion of the investigator or sponsor may lead to undue risk if study treatment were continued, such as the following:
 
 • Poor control or persistent activation of secondary atopic disease (eg, atopic dermatitis, asthma). • Development of biopsy-documented eosinophilic esophagitis.

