8.4.1 Assessment of Anaphylaxis

Anaphylaxis is a severe, potentially life-threatening systemic allergic reaction that occurs suddenly after contact with an allergy-causing substance ([Sampson, 2006](#)). The definition of anaphylaxis is met when any of the 3 criteria for suspected anaphylaxis in [Table 8](#) are fulfilled and the adverse event is grade 3 or higher per the systemic allergic reaction severity grading system ([Section 8.6](#)).

Systemic allergic reactions that do not meet both the criteria in [Table 8](#) and severity grade ≥ 3 per the systemic allergic reaction grading system ([Section 8.6](#)) will not be defined as anaphylaxis.

Adverse events of anaphylaxis are considered adverse events of interest and require rapid reporting as described in [Section 8.8.2](#).

Table 8: Protocol Criteria for Definition of Anaphylaxis

1. Acute onset of an illness (minutes to hours) with involvement of the following: 
• Skin, mucosal tissue, or both (eg, generalized hives, pruritus or flushing, swollen lips/tongue/uvula) and at least 1 of the following:	
a. Respiratory compromise (eg, dyspnea, wheeze/bronchospasm, stridor, reduced PEF, hypoxemia)b. Reduced blood pressure or associated symptoms of end-organ dysfunction (eg, hypotonia, syncope, incontinence)
2. Two or more of the following that occur rapidly after exposure to a likely allergen for the subject (minutes to hours):	
a. Involvement of the skin/mucosal tissue (eg, generalized hives, itch/flush, swollen lips/tongue/uvula)b. Respiratory compromise (eg, dyspnea, wheeze/bronchospasm, stridor, reduced PEF, hypoxemia)c. Reduced blood pressure or associated symptoms (eg, hypotonia, syncope, incontinence)d. Persistent gastrointestinal symptoms (eg, nausea, crampy abdominal pain, vomiting)
3. Reduced blood pressure after exposure to a known allergen for the subject (minutes to hours) as follows:	
a. Infants and children: $> 30\%$ decrease from baseline in systolic blood pressure or low systolic blood pressure defined as follows:
– Age 1-10 years: $< (70 \text{ mm Hg} + [2 \times \text{age}])$– Age 11-17 years: $< 90 \text{ mm Hg}$b. Adults (age ≥ 18 years): systolic blood pressure $< 90 \text{ mm Hg}$ or $> 30\%$ decrease from baseline

Source: Adapted from [Sampson, 2006](#).

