Systemic allergic reaction including any of the following signs and symptoms from 2 or more body systems: 
 Cutaneous: generalized pruritus, generalized urticaria, generalized flushing, angioedema (not laryngeal) Conjunctival: injection or pruritus Upper airway: rhinitis, cough (unrelated to laryngeal edema or bronchospasm) Gastrointestinal: nausea, mild abdominal pain, vomiting, or diarrhea 	Systemic allergic reaction involving 1 or more of the following: 
 Lower airway: (wheezing, chest tightness, dyspnea) Gastrointestinal: moderate abdominal pain or persistent vomiting or diarrhea 	Systemic allergic reaction involving 1 or more of the following: 
 Upper airway: laryngeal edema with stridor Lower airway: (wheezing, chest tightness, dyspnea) with cyanosis or hypoxia (O_2 saturation $\leq 92\%$) Cardiovascular: clinically significant hypotension [1] without end-organ dysfunction 	Systemic allergic reaction involving 1 or more of the following: 
 Lower airway: respiratory compromise (dyspnea, wheeze, bronchospasm, hypoxemia) requiring mechanical support Cardiovascular: hypotension [1] with associated symptoms of end-organ dysfunction (eg, hypotonia [collapse], syncope) 	Death

The protocol criteria for systemic allergic reaction are provided in [Section 8.4](#). The site of allergen exposure should be considered during the assessment of a systemic versus local reaction.

[1] Reduced blood pressure after exposure to a known allergen for the subject (minutes to hours) as follows:
 Infants and children: $> 30\%$ decrease from baseline in systolic blood pressure or low systolic blood pressure defined as follows:

- Age 1-10 years: $< (70 \text{ mm Hg} + [2 \times \text{age}])$
- Age 11-17 years: $< 90 \text{ mm Hg}$

 Adults: (age ≥ 18 years): systolic blood pressure $< 90 \text{ mm Hg}$ or $> 30\%$ decrease from baseline

Severity of all other adverse events (including adverse events considered allergic reactions that are not systemic allergic reactions) will be graded according to the general adverse event grading system. Adverse events will be graded 1 to 5 and have unique clinical descriptions of severity for each adverse event based on the general guideline presented in [Table 10](#). Full details of the general adverse event grading system are provided in the study manual.

Table 10: General Adverse Event Grading System

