Recurrent mild symptoms during several days of dosing at home suggest that the study product dose level is likely not tolerated, even if the symptoms meet the tolerability criteria. For mild dose-related symptoms occurring \geq 7 times within 2 weeks, the dose level is to be considered not tolerated. Isolated mild oropharyngeal pruritus occurring \geq 7 times within 2 weeks may not lead to an assessment of not tolerated for the dose level; tolerability of the dose level should be discussed with the medical monitor.

Moderate symptoms: A study product dose associated with moderate symptoms will be assessed as not tolerated, except on rare occasions such as a transient, self-limited symptom in a single organ system that requires no intervention, resolves completely, and is typically subjective.

If a study product dose associated with moderate symptoms is assessed as tolerated by the investigator, an explanation must be provided on the case report form.

Severe symptoms: A study product dose associated with severe symptoms will be assessed as not tolerated.

Life-threatening symptoms: A study product dose associated with life-threatening symptoms will be assessed as not tolerated.

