Moderate	
Administer the previous tolerated dose of study product at the study site at the time of the next dose.
 
 • If no symptoms occur with the reduced dose, continue that dose level for 2 weeks before attempting re-escalation. • If mild symptoms occur at the reduced dose, follow the guidelines for mild symptoms. • If moderate symptoms occur at the reduced dose, give a second reduced dose (1 or 2 dose levels lower) the next day at the study site. 
 – If the second reduced dose is tolerated, continue that dose level for at least 2 weeks before attempting re-escalation. – If mild symptoms occur with the second reduced dose that is assessed as not tolerated, follow the guidelines for mild symptoms. – If moderate symptoms recur at the second reduced dose, discuss early discontinuation with the medical monitor. 
 ▪ If a third reduced dose is considered to be safe after discussion with the medical monitor, give it at the study site under medical supervision. If the dose is assessed as not tolerated, stop study product dosing and discontinue the subject early from the study (Section 5.3). 
In the rare case that a dose with moderate symptoms is assessed as tolerated, follow the guidelines for mild symptoms and provide a brief explanation for the assessment in the subject's source documents.

Severe	
Discuss early discontinuation with the medical monitor. If continuation of study product is considered to be safe, administer a reduced dose at 2 dose levels at the time of the next dose at the study site under medical supervision. If the reduced dose is tolerated, continue that dose level for at least 2 weeks before attempting re-escalation. If the reduced dose is assessed as not tolerated, stop study product dosing and discontinue the subject early from the study (Section 5.3).
 
If the symptoms were associated with a modifiable risk factor that has resolved, the dose may be reduced by 1-2 dose levels at investigator discretion.
 
Stop study product dosing and discontinue the subject early from the study if the subject has anaphylaxis that requires intensive treatment.

Life-threatening	
Stop study product dosing and discontinue the subject early from the study (Section 5.3).

Assess dose tolerability per [Section 8.7.1.1](#).

GI, gastrointestinal.

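### The up-dosing and maintenance algorithm omits Table 4's mandatory stop for recurrent severe reactions, and Table 4 puts no grade on its stop for anaphylaxis with hypotension

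*Protocol*

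**What the plan says.** **Mandatory criteria (Section 5.3, Table 4).** Two examples of events for which subjects must discontinue matter here. The first is "Life-threatening symptoms, including anaphylaxis resulting in hypotension, neurologic compromise, or mechanical ventilation related to study treatment or food challenge". The second is severe dose-related symptoms that require intensive therapy, which by investigator assessment "may include interventions such as IV epinephrine, intubation, or admission to an intensive care unit) or are recurrent". A later item adds a stop when one dose reduction after severe symptoms is not tolerated.

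**Algorithm for up-dosing and maintenance (Section 8.7.3.2).** The Table 13 Severe row opens with a discussion of early discontinuation with the medical monitor. It goes on: "If continuation of study product is considered to be safe, administer a reduced dose at 2 dose levels". Then: "If the reduced dose is tolerated, continue that dose level for at least 2 weeks before attempting re-escalation". It stops dosing if the reduced dose is not tolerated or if anaphylaxis needs intensive treatment. The Table 14 epinephrine row covers dose-related symptoms including anaphylaxis. It provides for a next, reduced dose at the site and possible re-escalation, requires medical monitor discussion for severe symptoms, and stops at three or more epinephrine administrations for one event. The section's stop list has only two items: three consecutive failed escalation attempts, and reductions not tolerated after three attempts.

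**Grading.** Table 9 (Section 8.6) places "clinically significant hypotension [1] without end-organ dysfunction" in Grade 3 (Severe); hypotension with end-organ dysfunction is Grade 4 (Life-threatening). Section 3.4 counts AR201-related "anaphylaxis resulting in hypotension, neurologic compromise, or mechanical ventilation (systemic allergic reaction grading system grade ≥ 3 per" Section 8.6 towards suspending the study.

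**The concern.** A site managing a reaction during up-dosing or maintenance will work from Tables 13 and 14. Those tables repeat one half of Table 4's rule on severe reactions (intensive treatment) and leave out the other half (recurrence). Nothing in Section 8.7.3.2 says that the Table 4 criteria take precedence. Section 8.7.6.4 points only to Table 13 for severe symptoms in these periods. The operative algorithm is therefore less protective, as written, than the mandatory rule.

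The hypotension bullet raises a different problem. It names hypotension without a grade, under words that elsewhere in the protocol denote Grade 4, while Section 3.4 attaches grade 3 or higher to the same phrase.

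Subject safety is at stake in a first-in-human study enrolling from age 4, where reduced doses generally continue at home after a supervised first dose. So is consistent classification of outcome: Section 10.5.1 counts a subject who discontinues before the exit food challenge as a nonresponder, so uneven application of the stop can change the primary endpoint for that subject.

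**Working it through.** The check is a comparison of the rules, followed by two short worked cases.

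**Side by side**

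| Situation in up-dosing or maintenance | Table 4 | Tables 13 and 14, stop list | Result |
|---|---|---|---|
| Grade 4 reaction | Stop | Stop | Agree |
| Anaphylaxis needing intensive treatment | Stop | Stop | Agree |
| Three or more epinephrine doses for one event | Stop | Stop | Agree |
| Severe reaction at the reduced dose itself | Stop | Stop | Agree |
| Severe reaction recurring after a tolerated reduction, no intensive treatment | Stop (recurrent) | No stop named; Severe row applies again | Omission |
| Anaphylaxis with Grade 3 hypotension, no intensive treatment | Depends on reading | Reduced dose if judged safe | Ambiguity |

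The fourth row agrees because Section 8.7.1.1 says "A study product dose associated with severe symptoms will be assessed as not tolerated", and Table 13 then stops dosing. Table 4 lists that situation separately, so its recurrence wording must reach further. A severe reaction at re-escalation or later, after a tolerated reduction, is the natural case.

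**Recurrence: severe reactions before a mandatory stop.** Assumptions: recurrent, which the protocol does not define, means a second severe reaction; every reduced dose is tolerated; continuation is judged safe each time; no event needs intensive treatment or three epinephrine doses.

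- Table 4: stop at reaction 2.
- Section 8.7.3.2 alone: the only count-based stop left is three consecutive failed escalation attempts at least 2 weeks apart. If the first reaction is itself a failed escalation, the stop comes at reaction 1 + 2 = 3. If it occurs at a level already reached, the stop comes at 1 + 3 = 4.
- The shortest time from first to third failed attempt is 2 × 2 = 4 weeks.
- A tolerated intermediate step (200 to 240 mg) could break the run of consecutive failures and push the stop later.
- The epinephrine limit is per event and does not accumulate across reactions.

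**Hypotension: one illustrative event.** An 8-year-old on 300 mg has generalized hives and a systolic pressure of 84 mm Hg, without end-organ dysfunction, and recovers after one intramuscular epinephrine injection.

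- Table 9 threshold: 70 + 2 × 8 = 86 mm Hg. Since 84 < 86, this is Grade 3 hypotension.
- Skin involvement plus reduced blood pressure meets Table 8 criterion 1. With Grade 3 it is protocol-defined anaphylaxis.
- Table 6 (Section 8.3) says one or two intramuscular injections are typically not intensive therapy, so the Table 13 intensive-treatment stop would not normally apply.
- Table 4, if its first bullet reaches Grade 3: discontinue. If the bullet is confined to Grade 4: no mandatory stop for a first event.
- Tables 13 and 14: after medical monitor discussion and only if judged safe, 200 mg (two levels below 300 mg in Table 3) at the site. That dose is held at least 2 weeks under Table 13, or for the time the investigator recommends under Table 14, and re-escalation may then be attempted.
- If AR201-related, the same event counts towards the Section 3.4 limit of more than 2 cases.

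**The case against.** The strongest reply has four parts.

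1. **Table 13 is silent on recurrence; it does not permit it.** No sentence there says dosing may continue after a recurrent severe reaction. Section 5.3 applies throughout treatment, Section 8.7.3.2 lists discontinuation under Section 5.3 among its actions, and the Severe row's first instruction is to discuss discontinuation. This stands: a reader might infer that the two tables contradict each other, and the text does not support that. It shows an omission from the algorithm of a stop that Section 5.3 still imposes.

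2. **Life-threatening means Grade 4 elsewhere in the protocol.** Tables 9, 11, 12 and 13 all separate it from severe, and on that reading the first bullet matches Table 13's Life-threatening row. A reader might infer that Table 4 plainly requires a stop for Grade 3 hypotension; it does not do so plainly. The narrow reading is not secure either. The bullet lists hypotension apart from neurologic compromise and asks for no end-organ dysfunction. Section 3.4 ties the phrase to grade 3 or higher, though that may only restate the definition of anaphylaxis. Section 8.4.1 says "Anaphylaxis is a severe, potentially life-threatening systemic allergic reaction that occurs suddenly after contact with an allergy-causing substance", but potentially life-threatening is weaker than life-threatening.

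3. **Central checks exist.** Medical monitor discussion is required, and severe events and epinephrine use are reported within 24 hours. So it would be too strong to say that the outcome simply depends on which table a site opens. But the discussion in Table 13 turns on whether continuation is safe, a question that Table 4 closes for the events it lists.

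4. **Figure 3 is not visible.** The comparison is between table texts only, and the figure might address these cases. Section 8.7.3.2 does say that Table 13 describes the algorithm the figure shows.

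**Conclusion.** The point holds as an omission and an ambiguity, and should be fixed. The recurrence limb is the firmer: Table 4 mandates a stop that the Table 13 Severe row, the Table 14 epinephrine row and the stop list do not carry, and no text states that Table 4 overrides them. Followed as written, the algorithm can return to dosing a subject whom Table 4 requires to stop. The gap is reaction 2 against reaction 3 or 4, or later, under the stated assumptions; these are courses the text permits, not courses to be expected. The hypotension limb is an unresolved grade in one bullet, and the documents do not settle which grade was intended. They give no rate for either event with AR201, so no frequency is claimed.

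**What to change.** 1. Add to the Table 13 Severe row, with a cross-reference from the Table 14 epinephrine row: *Stop study product dosing and discontinue the subject early if a severe dose-related reaction recurs after a tolerated dose reduction (Section 5.3).*
2. State in Sections 8.7.3.2 and 8.7.6.4 that the mandatory criteria of Table 4 govern.
3. Put an explicit grade on the Table 4 hypotension bullet. Use grade 3 or higher to match Section 3.4, with a matching stop in the Table 13 Severe row. If the sponsor intends that continuation after Grade 3 hypotension should remain possible, use Grade 4 only.

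The cost is a few sentences and cross-references, with no new procedure or data. There may be a few more mandatory discontinuations, counted as nonresponders. With 56 AR201 subjects planned, each one lowers that arm's response rate by at most 1/56 = 1.8 percentage points.

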5.4 Study Exit

Study exit procedures are listed in [Appendix 5](#).

Completion of study exit procedures, including both days of the exit DBPCFC and attempting the open baked whole egg food challenge, will be considered as completing the study. Eligible subjects will have the option to enroll in an open-label, follow-on study to receive AR201 treatment until it becomes commercially available or product development is terminated. Blinded study treatment may continue in this study if the follow-on study is not yet available at the study site when subjects complete their course of treatment. The treatment assignment for each subject will be unblinded after study exit, after all major data

queries for the subject are resolved, and the open-label follow-on study is available at the study site.

Subjects with unresolved adverse events at study exit or who had GI adverse events of interest (ie, GI adverse events that result in dose interruption > 7 consecutive days or early discontinuation; [Section 8.7.6.2.1](#)) will have safety follow-up per [Section 5.5](#).

5.5 Safety Follow-Up

Safety follow-up procedures are listed in [Appendix 6](#).

Safety follow-up is for subjects with unresolved adverse events at early discontinuation or study exit, or who had GI adverse events of interest (ie, GI adverse events that result in dose interruption > 7 consecutive days or early discontinuation; [Section 8.7.6.2.1](#)). The duration of safety follow-up is as follows:

- Subjects who have unresolved adverse events at early discontinuation or study exit will have safety follow-up for 30 days or until consent for follow-up is withdrawn.
- Subjects who have unresolved serious adverse events at early discontinuation or study exit will have safety follow-up for 30 days or until the ongoing serious adverse events resolve or stabilize, whichever is last, or until consent for follow-up is withdrawn.
- Subjects who have GI adverse events of interest ([Section 8.7.6.2.1](#)) will have safety follow-up for at least 6 months or until consent for follow-up is withdrawn. For chronic or recurrent GI symptoms persisting after 6 months, follow-up will continue for up to 1 year or until chronic or recurrent GI symptoms resolve or consent for follow-up is withdrawn, whichever is first ([Section 5.5.1](#)).

For subjects who refuse to come to the study site or if safety follow-up cannot be obtained from alternate contacts, telephone contact must be attempted and documented to review for adverse events. The procedures for loss to follow-up will be followed for subjects or parent/caregivers who do not respond to telephone calls ([Section 5.6](#)).

